**Version Date: October 28, 2024**

**Principal Investigator: [name] CCC-SLP**

## PROTOCOL SYNOPSIS

This study is an investigation of the feasibility of administering, and quantifying the effects of a canine-assisted aphasia treatment entitled, the Persons with Aphasia Training Dogs Program. Individuals with aphasia are trained in using positive reinforcement techniques to train dogs in basic obedience skills. On program completion, participants are evaluated on their ability to use the techniques and are assessed for the effects of program participation on psychosocial aspects of living with aphasia and on cognitive-linguistic factors. It is hypothesized that 1) persons with aphasia will be able to independently cue a dog to perform basic obedience skills and that 2) participants will demonstrate increases in self-confidence and social engagement.

Participants self-select into groups based on interest and dog-status: a) PATD participants working with family dog or b) PATD participants working with PSPCA (Pennsylvania Society for the Prevention of Cruelty to Animals) shelter dogs. Guidance is provided relative to the fact that some interested participants may have a family dog that is not eligible to participate (e.g., bite history), in which case the participant would be invited to participate with PSPCA dogs. All PATD and behavioral assessment sessions are conducted individually, i.e., between an individual participant and members of the study team.

The program was previously run as an activity offered by the MossRehab Aphasia Center. The current study will enroll a minimum of 20 PATD participants and is informed by the PI's experience of administering the program and commensurate to the timeline and resources of the funding mechanism. For this feasibility study, data analysis will be performed using criterion-referenced benchmarks to assess within- subject effects and, for secondary analyses between-group (immediate vs. waitlist) differences where possible.

## SIGNIFICANCE

Aphasia is an acquired language impairment, most commonly resulting from stroke, that affects more than 2 million Americans. The hallmark impairment associated with aphasia is difficulty with word retrieval, which can sometimes be so severe that persons with aphasia (PWA) are able to produce only one or two words in an utterance. By definition, the language impairment in aphasia exists in the context of relative preservation of cognitive functioning, leaving PWA having retained their personality, their intellect, and their drive to engage with those around them trapped inside a brain that "knows what it wants to say, but just can't get it out".

Whereas the definition of aphasia highlights the linguistic impairments associated with aphasia, those living with aphasia often highlight its psychosocial consequences that include loss of identity (Musser et al., 2015; Shadden, 2004), loss of confidence (Babbitt, 2010), and social isolation (Davison et al., 2008; Vickers, 2010). Aphasia rehabilitation aligned with the principles of the life participation approach to aphasia (LPAA, Chapey et al., 2000) bridges the gap between rehabilitation of language skills and the use of those skills to engage in meaningful communication and activities. As first described by the "LPAA Working Group" in 2000, the LPAA emphasizes not only the need to facilitate communication for and with PWA, but to situate the use of communication skills in the context of the "real life" goals that PWA have for themselves relative to engaging with and participating in their communities (Chapey et al., 2000). To realize these goals, clinicians facilitate not only development of linguistic skills and strategies, but also reduction of barriers to community participation for PWA, both internal (e.g., reduced communicative confidence) and external barriers (e.g., community members reluctant to communicate with people with aphasia) (Simmons-Mackie & Damico, 2001; Simmons-Mackie & Kagan, 2007).

From the perspective of community (re-)engagement, canine-assisted treatment is perfectly suited to aphasia rehabilitation. People with aphasia often are 'punished' for their communication attempts, being ignored or actively rejected, when they have difficulty. In their role as social catalysts, dogs can promote social interaction

## Assessing an animal-assisted treatment program for adults with aphasia: the Persons with Aphasia Training Dogs (PATD) Program

by enticing potential communication partners and promoting communication partners' trust in the PWA accompanied by the dog (Beetz, 2017). In addition to providing an engaging presence to talk to and about, as non-judgmental recipients of care-taking and attention, dogs can increase positive mood, and feelings of self-efficacy and self-confidence, and contribute to improvements in self-perceived quality of life and ability to cope with stressful events (Beetz, 2017; Gee et al., 2018). The limited available evidence specific to PWA indicates PWA who participate in canine-assisted treatment report increased feelings of motivation to participate in and benefit from traditional language treatment offered in the presence of a dog, as well as experiencing more opportunities to practice communication when they are with the dog (Adams, 1997; LaFrance, 2007; Macauley, 2006). While compelling, the promise for benefit suggested by extant AAT studies with PWA is compromised by the same challenge noted in the wider AAT evidence base, a lack of replicable and manualizable methods (Gee, 2018; Morrison, 2007; O'Haire, 2015), such that there is little to no information specifying the procedures used during treatment and even less regarding the role of the dog, beyond being present, in facilitating any observed gains.

The gap in the AAT evidence base particularly with respect to PWA is striking also in light of the fact that PWA may be ideal candidates for canine-assisted treatment owing to a fundamental tenet of aphasiology that, "people with aphasia communicate better than they talk" (Holland, 1977). They achieve this "better" communication by capitalizing on their strengths. When their words fail them, a strength many PWA use to support communication is preserved pragmatic skill, including the ability to use and interpret tone of voice, facial expression, gesture or other 'body language' in the sharing of meaningful communication (Dronkers et al., 1998; Holland, 1977; Wulfeck et al., 1989). It is these types of skills that are critical in understanding and responding to dogs (Andics et al., 2016; Miklosi et al., 2003; Reid, 2009; Teglas et al., 2012). In this way, canine-assisted treatment for PWA provides for rehabilitation from a perspective of strength, capitalizing on what PWA can do and how that can be brought to bear in accomplishing what is most important to them. Our *Persons with Aphasia Training Dogs* program represents a convergence of 'what are strengths' and 'what is important', through creation of an animal-assisted treatment in which the strengths of PWA are brought to bear in a rehabilitation program designed to target what they report is important to them.

**We hypothesize that 1) PWA can learn the skills of positive reinforcement dog training, and 2) that new skill learning in the context of working with dogs will provide psychosocial benefits including increased self-confidence and social participation.** These hypotheses are supported by our preliminary data, and by evidence in the human-canine interaction and animal-assisted treatment literatures. The fact that the annual incidence of aphasia is anticipated to reach 180,000 by 2020, coupled with recent evidence that twenty percent of newly aphasic individuals report having no friends six months post-stroke (Simmons-Mackie, 2018), brings into sharp relief the need for rehabilitation that addresses the psychosocial consequences of aphasia. Animal-assisted treatment (AAT) is an ideal service delivery model, providing PWA the physical and psychological benefits of animal companionship along with dogs' ability to act as 'social catalysts' (Beetz, 2017) for engagement with others in the community. As such, there is a compelling need to fill the striking gap in the evidence-base regarding the efficacy of AAT in the rehabilitation of PWA. Our team is well-positioned to contribute to filling this gap, with the PI, an experienced aphasiologist with years of experience using positive reinforcement techniques to train dogs, working with experts in clinical aphasiology, cognitive neuropsychological rehabilitation, and canine behavior. The results of this study are expected to demonstrate the feasibility of administering, and quantifying the effects of, a canine-assisted aphasia treatment. Considering the large number of American households that include dogs (estimated 48.3 - 63.4 million), the growing interest in incorporating AAT into rehabilitation with clinical populations across service delivery settings (HABRI Central Brief, 2016; Hediger et al., 2019; Hediger & Hund-Georgiadis, 2017; Linder et al., 2017; Matuszek, 2010; McCullough et al., 2016; Munoz Lasa et al., 2015; Thodberg, Berget, & Lidfors, 2014), and the accessibility of this treatment to a wide variety of PWA, this treatment has the potential to have a substantive **positive impact** on a large number of Americans living with aphasia. This project is a crucial first step toward our **long-term goal** to augment the evidence base with what O'Haire and colleagues (2015) deem, "research [that is] essential to establish feasibility, efficacy, and manualizable protocols" (p. 1) for AAT and that target the psychosocial consequences of aphasia.

**Innovation:** The PATD program represents a novel understanding of what constitutes health care, engaging participants in an animal-assisted treatment program to address the communication and psychosocial needs of PWA through engagement in rehabilitation that occurs within the community itself. We are aware of no

## Assessing an animal-assisted treatment program for adults with aphasia: the Persons with Aphasia Training Dogs (PATD) Program

program of this kind for persons with aphasia, nationally or internationally, in which dog training is conceptualized as AAT in service of psychosocial outcomes and participants' own community engagement goals. That said, we are encouraged by evidence of the success of similar programs for other clinical populations (Yeager & Irwin, 2012). This project represents the first systematic investigation of the effectiveness of AAT for rehabilitation with PWA. This work will provide a critical first step toward filling this gap as well as providing a much-needed model for operationalizing AAT.

### APPROACH

Accomplishment of the overall objective of this application will be achieved through this small-scale, feasibility study aimed to garner preliminary support for our hypotheses and to provide the foundation for a future, large-scale clinical trial.

**Specific Aim 1: Determine whether PWA, through participation in the PATD program, can learn and implement positive reinforcement techniques to train dogs in basic obedience skills.** *Hypothesis 1:* On program completion, PWA will be competent in using positive reinforcement techniques, to independently cue a dog to complete a minimum of 4 (of 5) trained obedience skills. To test this hypothesis, we will assess program participants using a PI-adapted version of the *Pet Partners® Animal-Handler Evaluation*.

**Rationale:** Our first hypothesis is supported by the fact that positive reinforcement dog training capitalizes on the pragmatic skills that may be accessed by individuals with aphasia even in the presence of severe language production impairment. Positive reinforcement training is based on the principle of reward-based associative learning, in which the dog learns to associate her performance of certain actions with a reward (e.g., food, praise in a happy tone of voice, toy, etc.) (Hiby et al., 2004; Perry & Conza, 2012; Pryor, 2006). Two of the most important components of the training are shaping of behavior and timing. *Shaping* (or successive approximation) might be described as helping the dog understand what you want her to do and is often achieved through the use of gestural cues. For example, when training SIT, a treat lure might be held above the dog's nose and slowly moved backward over her head, which, as the dog follows the treat with her eyes and nose, facilitates her putting her bottom on the ground. Similarly, when training TOUCH, i.e., the dog touches your open palm with her nose, you might first hold your 'hot-dog-smelling' hand quite close to her nose to make it 'obvious' to her. As she becomes faster with responding to the open palm cue, you move your hand farther back to make it more difficult. In this way, you proceed in a stepwise, sequential manner from the easiest iteration of the command to the more difficult, such that the dog learns to respond to each hand cue with the associated behavior. Because the dog is being trained through the use of cues to learn to associate her behavior with attainment of a reward, *timing* is critical. The trainer's attention must be focused on sometimes minute changes in the dog's posture or gaze so that the desired behavior can be captured or marked as soon as it occurs. A common marker is the 'click' of hand-held clicker device, which provides a brief but immediate, salient, and consistent signal to the dog that can then be followed by the slower process of providing the treat. These techniques are well-suited to use by PWA. The training itself can be easily depicted or modeled, if necessary, the person with the language impairment may learn through demonstration rather than lengthy verbal explanation. The use of hand signal cues and a clicker to mark the desired behavior remove the need for even single word production, but do not *restrict* use of verbal cues and other vocabulary if a goal for the PWA is to improve retrieval or production of this vocabulary. As such, the principles and techniques used in positive-reinforcement training are accessible to PWA. The procedures employed in training can also be adapted for those with the right-sided hemiplegia that often accompanies stroke. In addition to the fact that PWA retain the skills to work with dogs, evidence suggests that the presence of the dog "promotes the pre-conditions for learning" (Beetz, 2017, p. 7), reducing distraction and stress, while increasing intrinsic motivation (Beetz, 2017).

## Assessing an animal-assisted treatment program for adults with aphasia: the Persons with Aphasia Training Dogs (PATD) Program

**Skills Training:** In consultation with a certified professional dog trainer, the PATD program was developed by the PI, a trained speech language-pathologist with more than eighteen years of experience working with people with aphasia, who has spent more than ten years working with shelter animals using positive reinforcement techniques.

Participants enrolled in the PATD program will engage in five once-weekly individual training sessions with the PI, either with a family dog (PATD) or by volunteering at a local shelter, the Pennsylvania SPCA (PATD-PSPCA). PATD-PSPCA participants will work only with dogs that have been evaluated by PSPCA staff as appropriate for interaction with new volunteers. Each session will be dedicated to one of five pre-determined, sequentially-presented, obedience skills (i.e., LOOK, TOUCH, SIT, STAY, COME). Training sessions will last approximately 75 minutes, with an additional half hour allotted to the beginning of the first training session to review principles of positive-reinforcement training. Subsequent sessions will begin with a brief probe of the participant's skill in cueing the dog to perform the behavior trained the previous week. Following the probe, sessions will continue with a review of that week's lesson plan (Figure 1), after which the PI will model the first training step three times. After the model has been provided, the participant will attempt the procedure, receiving instructive feedback or reinforcement from the trainer. Instruction will proceed to the subsequent step when the participant and dog have attained 5 successful trials at the current step. The same demonstration procedure will be used at each subsequent step. Commands will be trained using one hand gesture for each behavior. To mark behaviors, participants will use a clicker attached to a wrist band, which can be hand-held or allowed to dangle for ease of use for those with hemiplegia. Participants will have the option of introducing the verbal command, but will not be required to do so. All participants will be asked to provide their dog with a walk before training sessions to support the dog in being ready to participate.

**Skills Practice:** Participants will not be required to complete all steps for an obedience skill in a single session, and will be encouraged to practice the skill with the dog for at least 3 practice sessions over the course of the week. Practice will be used as a measure of participant compliance. Each participant will be provided with a copy of the lesson plan and, if interested, a video demonstrating the PI performing the target skill with her own dog. Participants will also be provided with a training log to complete after each time they practice over the course of the week. Using a nine-point visual analog scale adapted from the *Assessment of Living with Aphasia* (ALA) (Simmons-Mackie et al., 2014), participants will rate their own and the dog's performance during each practice session (see *PATD Practice Log*, in Appendix). To facilitate responses on the log, participants will practice self-reflection with the PI during training sessions (e.g., "How many times did I have to cue the dog?", "Did I 'click' as soon as the dog did what I asked?").

**Skills Evaluation:** In consultation with a CPDT who is a practitioner of positive reinforcement training, the PI-adapted *Pet Partners® Animal-Handler Evaluation (PPAHE)* will be used to evaluate handler competence, on parameters associated with shaping and timing, on a scale of 0 ("not ready") to 2 ("best") (see blank *PPAHE* in Appendix). Weekly single-skill probes will be conducted by the PI/trainer but will be scored via video-recording by a certified professional dog trainer (CPDT). Summative assessment of all skills will occur twice, within one week of training completion and at a 3-month follow-up. Summative assessments will be completed in person by a CPDT who will also score the weekly formative evaluations via video-recording. To maintain scientific rigor, the CPDT will score probe evaluations via video after the follow-up in person summative evaluation has been completed. As reflected in the adapted *PPAHE*, scores will be based solely on participants' competence

**MossRehab Aphasia Center  
PATD Program**

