**Expected results:** It is expected that participants will be able to independently cue a dog to perform a minimum of 4 out of 5 obedience behaviors. It is also expected that the median cumulative score will be at least 5, which corresponds with achieving a minimum of a 1 ("ok") on all five targeted obedience behaviors or achieving a 2 ("best") on at least one behavior and 1 on three others.

**Scientific rigor:** To maintain treatment fidelity, all PATD training will be conducted by the PI. PATD training sessions will be digitally video recorded. Control for experimenter bias will be achieved by having skill probes scored via video-recording by one CPDT, and having summative evaluation conducted and scored by a second CPDT. The PI will not be present for the summative evaluations. For the purposes of establishing inter-rater reliability, summative evaluations will be digitally video recorded so that a third CPDT can independently evaluate participant performance. PSPCA participants may work with a different dog each week to accommodate for the fact that the same dog may not be available for training from week to week. All CPDTs will be practitioners of positive reinforcement training, the cuing and shaping techniques for which are relatively standard and are familiar to practitioners of the technique.

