
Participants will be encouraged to practice the skill in 3 practice sessions over the course of the week. Participants will be instructed that each practice session should not last longer than approximately 30 minutes and that breaks for play, drinking water, sniffing-walks, should be provided as needed. Practice sessions may also be broken up into shorter increments (e.g., three 10-minute sessions, six 5-minute sessions). Practice will be used as a measure of participant compliance. PATD-participants will be provided with aphasia-friendly written materials including: 1) lessons plans, 2) practice log sheets, and 3) practice reminders. They may also be provided with example videos of the PI performing the obedience skills with her own dog. PATD-participants will be informed that at the beginning of the subsequent training session, the PI will be evaluating their ability to cue the behavior introduced the previous week using a PI-adapted *Pet Partners® Animal-Handler Evaluation*

Assessing an animal-assisted treatment program for adults with aphasia:  
the Persons with Aphasia Training Dogs (PATD) Program

(adapted *PPAHE*) will be used to rate handler cueing on a scale of 0 (“not ready”) to 2 (“best”). Progression to training of each behavioral skill will not be contingent on evaluation of the previous skill.

After each training session, the participant will be provided with a copy of the appropriate lesson plan, three participant practice logs, and, if interested, a video demonstrating the PI performing the target skill with her own dog. As study staff will not be present for practice sessions, participants will be instructed on behaviors to watch for that indicate the dog might need/want a break or to stop practice for the day, e.g., signs of fatigue (e.g., inattention, disinterest in interaction) or distress (e.g., tail tuck, ears flat/back, avoidance). PSPCA participants will be instructed to practice with the same dog with whom they trained on each skill. If that dog is not available, they will be instructed to work with another dog who has been labeled by PSPCA staff to be at (or easier than) their current level of proficiency as determined by the PSPCA (e.g., beginner volunteers may only work with beginner-appropriate dogs).

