### Overall Structure of the Study Team

The study team will consist of the PI, the study research assistant (RA), the certified professional dog trainers (CPDT) and the study speech-language pathologists (SLP). The PI will conduct PATD dog probe and training sessions. CPDTs will conduct and review video recordings of the probe and in-person cumulative evaluation sessions, during which the PI will not be present. A second staff member may be present during all PATD sessions to video-record the sessions. The RA may assist with recruitment, scheduling, and data collection (including video recording) and analysis. One SLP will conduct behavioral assessment sessions and a second SLP will score study instruments and code video-recordings of narrative interviews.

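### The protocol assigns probe and summative scoring to one dog trainer in one place and to two in another; under the one-rater text the claimed rater independence is lost for the weekly probe scores

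*Combined protocol and SAP*

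**What the plan says.** Four places in the combined protocol and SAP bear on who produces the scores on the adapted Pet Partners evaluation.

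- **Specific Aim 1, Skills Evaluation.** The PI/trainer runs the weekly single-skill probes. Scoring is described thus: "Summative assessments will be completed in person by a CPDT who will also score the weekly formative evaluations via video-recording". The timing rule follows: "the CPDT will score probe evaluations via video after the follow-up in person summative evaluation has been completed". Summative assessments take place within a week of the end of training and again at 3 months.
- **Specific Aim 1, Scientific rigor.** Experimenter bias is to be controlled by "having skill probes scored via video-recording by one CPDT, and having summative evaluation conducted and scored by a second CPDT". The same paragraph adds "The PI will not be present for the summative evaluations", and has a third CPDT rate the summative recordings for inter-rater reliability.
- **Study Procedures and Materials.** Participants are told that at the next session "the PI will be evaluating their ability to cue the behavior introduced the previous week".
- **Overall Structure of the Study Team.** The PI is said to conduct the probe and training sessions. The next sentence reads: "CPDTs will conduct and review video recordings of the probe and in-person cumulative evaluation sessions, during which the PI will not be present".

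The probe scores have one planned use. In the Aim 1 Statistical Considerations, repeated in Statistical Design and Power, they are dichotomised as 0 versus 1 or 2 and enter a repeated measures logistic regression, which is a secondary analysis. Neither of those sections names a rater.

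**The concern.** Skills Evaluation and Scientific rigor are both current text, both are offered as safeguards, and they describe different staffing. A team that follows Skills Evaluation will not deliver the separation of raters that Scientific rigor claims, and a report that repeats Scientific rigor would then describe a control that was not in place.

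What is at stake is the weekly competence analysis, which is meant to show how competence changes over time. Under the one-rater text, the person scoring an early probe has already examined the same participant on all five skills, twice. Knowledge of how someone finished can colour a judgement of how they started, in either direction. The rating is a three-level judgement of shaping and timing, and the analysis cuts it between 0 and 1. A one-step shift at that cut therefore changes the analysed outcome, while a shift between 1 and 2 does not.

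**Working it through.** No stated sample size, interval or error rate depends on this point, so there is no figure of the plan's to reproduce. The check is a comparison of texts and a count.

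**1. Can the two texts be read together?**

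| Question | Skills Evaluation | Scientific rigor |
|---|---|---|
| Who conducts and scores the summative evaluations? | A CPDT | A second CPDT |
| Who scores the probe videos? | The same CPDT | A different CPDT |
| What is the safeguard? | Probes scored after the 3-month evaluation | Separation of the two raters |

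The timing rule in Skills Evaluation has a clear purpose only if one person does both jobs: it stops probe scoring from colouring the summative score. Scientific rigor makes the separation itself the control: "Control for experimenter bias will be achieved by having skill probes scored via video-recording by one CPDT", with the summative work given to someone else. One text has to give way.

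**2. Does another section decide it?** No. Overall Structure of the Study Team speaks of CPDTs in the plural without assigning tasks to individuals. Study Procedures and Materials names only the PI. Statistical Design and Power names nobody.

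**3. How many scores are exposed under the one-rater text?**

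- Training sessions per participant: 5 (Skills Training; Study Procedures and Materials).
- Probes open the sessions after the first and test the previous week's skill, so probes per participant = 5 − 1 = 4 (LOOK, TOUCH, SIT, STAY).
- Participants: 20, the planned minimum, all assumed to complete.
- Probe scores = 4 × 20 = 80.

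No weekly probe of COME is described; the schedule goes from Skill 5 to the post-training evaluation. If a fifth probe were added, the count would be 5 × 20 = 100. In both cases the exposed share is all of them, because every probe is scored after that participant's follow-up evaluation.

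**4. Would the plan detect carry-over into the probe scores?** The third CPDT rates summative recordings only. The reliability sample of about 20% is described under Aim 2 for the speech-language pathology assessments, with a second speech-language pathologist. No second rating of probes is described.

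**5. Which analyses can be affected?** Under the one-rater text, information can pass only from the summative evaluations to the probes, because the probes are scored last. That reaches the repeated measures logistic regression. It does not reach the proportion of participants who successfully complete training, if that is derived from the summative score, or the median cumulative score.

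**The case against.** The strongest reply is that the one-rater text has a deliberate safeguard of its own. Scoring probes last protects the outcome that matters most, the scorer is still a CPDT and not the PI who delivered the training, the PI is kept out of the summative evaluations, and a third CPDT checks the summative ratings. All of that stands. A reader might infer that under Skills Evaluation no control of experimenter bias is left, or that the primary result is compromised. The documents support neither inference. What is lost is independence between the probe rater and the summative rater.

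A second reply is that the PI's role is less muddled than it looks. Skills Evaluation is explicit that the PI runs the probes and a CPDT scores them. The sentence in Overall Structure of the Study Team can be read as CPDTs reviewing probe videos and conducting the cumulative evaluations. The statement in Study Procedures and Materials reports what participants are told. This largely stands: nothing says that a PI rating enters the analysis, and these two places need only clearer wording.

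A third reply is that no comparison of probe scores with summative scores is planned, so their dependence spoils no prespecified agreement analysis. That is correct, and the concern does not rest on one.

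Finally, the two-rater text is not itself a full answer. It separates the raters but does not say that the probe rater is unaware of the summative results, so it cannot be credited with removing all exposure.

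**Conclusion.** The inconsistency is real and unresolved. If staff follow Skills Evaluation, the rater independence claimed in Scientific rigor is absent, and all the weekly probe scores (about 80) come from a rater who has already seen each participant's final performance, with no described check on those scores. The consequence is confined to a secondary analysis. It should be corrected, but it does not threaten the primary proportion.

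This rests on three assumptions: that 20 participants complete, that only the four described probes are taken, and that successful completion is judged from the summative score, which the Aim 1 Statistical Considerations imply but do not state outright. The size and direction of any shift in probe scores cannot be estimated from the documents.

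**What to change.** - **Skills Evaluation:** rewrite to match Scientific rigor. CPDT A scores probe videos only and is masked to summative results. CPDT B conducts and scores both summative evaluations. The third CPDT's reliability rating stays as it is.
- **If one rater is kept instead:** rewrite the bias-control claim in Scientific rigor to rest on what would remain (scoring order, PI absence, the third rating of summative videos), and state that probe scores were given with knowledge of the final performance.
- **Study Procedures and Materials:** say that the PI administers the probes and that no PI rating enters the analysis.
- **Overall Structure of the Study Team:** reword, without deleting, so that CPDTs review probe videos and conduct the cumulative evaluations without the PI. The sentence is needed because it assigns the summative role.

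Stripping week labels from the probe clips would add little: skills are taught in a fixed order, so the skill shown reveals the week. Masking to summative results is the part that matters.

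The cost is a wording amendment and some reassignment of scoring among CPDTs already provided for. With separate raters, probe scoring would no longer need to wait for the 3-month evaluation.
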